9.3.5 Interim Monitoring

Study data will be reviewed by DSMC twice a year during the first 2 years of study activation, and once a year thereafter upon their approval if the study goes smoothly. Two formal interim efficacy analyses on the primary endpoint will be performed, after approximately one third and two thirds of the patients have completed study treatment and IFI observation. Monitoring boundary for the primary endpoint on IFI will be based on Lan-Demet's method with spending function α^2 .

At the time of primary efficacy monitoring, the observed incidence of IFI during the first 42 days following HCT in patients randomized to the comparator arm will be monitored. If the 95% 1-sided confidence interval does not contain the assumed rate of 7%, the study will be referred to DSMC for consideration of study closure. Roughly speaking, if ≤ 2 IFI out of 93 patients, or ≤ 7 out of 187 patients, the rule will be met. However, the exact rule at the time of monitoring will depend on the exact N at the time of the interim analysis and whether there is censoring and how much. If no censoring and exactly at the numbers listed above, the rule will be those above.

Informal safety analyses will also be performed on the observed adverse events at each DSMC review. This analysis will include all patients who receive at least one dose of study medication. The proportion of patients experiencing any reportable grade 4 or higher adverse event will be compared between the 2 arms using chi-square tests. For such informal safety analyses, each test will be at two-sided level of 0.05 without adjustment for multiple testing. If a significant difference between the 2 arms is found ($P < .05$), the study committee will perform a review of the adverse event profiles and report the finding to DSMC for their evaluation, with a recommendation about action with respect to the study.

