Assuming the incidence of IFI during the period at risk for the primary objective (Day 0 to Day 42) is 7% in the control patients (with fluconazole or voriconazole) and that the incidence of IFI is 2% with caspofungin prophylaxis, we will require 560 randomized patients (approximately 280 per arm) to achieve 80% power at 2-sided alpha level of 0.05. The power consideration is based on a 2-sample log rank test comparing the time to (first occurrence of proven/probable) IFI. Time to IFI is assumed to follow an exponential distribution. The observation period for the primary endpoint is from Day 0 till Day +42 following high-risk allogeneic HCT. Under an exponential time-to-IFI model with these parameters, the incidence of IFI is distributed almost evenly during the at-risk period; for each one-third of at-risk period (~14 days), the incidence of IFI is 2.3%-2.4% for patients on the azole arm and is 0.66%-0.67% for patients on the caspofungin arm. A 5% exponential loss-to-follow-up during the at-risk period is also included in the power consideration. Considering up to 5% of the enrolled patients might be deemed ineligible, the maximum enrollment number is adjusted to 590. The expected number of IFI among 280 eligible azole arm patients is 19.6.

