11.4 Routine Adverse Event Reporting

Note: The guidelines below are for routine reporting of study specific adverse events on the COG case report forms and do not affect the requirements for **CTEP-AERS** S reporting.

The NCI defines both routine and expedited AE reporting. Routine reporting is accomplished via the Adverse Event (AE) Case Report Form (CRF) within the study database. For this study, routine reporting will include all toxicities reported via **CTEP-AERS** and all Grade 4 and higher non-hematological Adverse Events.

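### The one planned between-arm safety test does not exclude invasive fungal infection, so caspofungin's expected benefit can partly mask a caspofungin toxicity excess

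*Combined protocol and SAP*

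**What the plan says.** Section 9.3.5 describes an informal safety analysis at each DSMC review: "The proportion of patients experiencing any reportable grade 4 or higher adverse event will be compared between the 2 arms using chi-square tests". On the population it says "This analysis will include all patients who receive at least one dose of study medication". On error control it says "each test will be at two-sided level of 0.05 without adjustment for multiple testing". A result below the 0.05 level leads to this step: "the study committee will perform a review of the adverse event profiles and report the finding to DSMC for their evaluation". The committee also advises on what the trial should do next. On timing: "Study data will be reviewed by DSMC twice a year during the first 2 years of study activation", then yearly if the study runs smoothly.

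Section 11.4 defines what is routinely reported: everything sent through CTEP-AERS, plus "all Grade 4 and higher non-hematological Adverse Events". Table B in Section 11.3 adds every death within 30 days of the last dose, whatever its cause, and unexpected grade 4 events that are at least possibly related to the drug.

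IFI is collected separately, through the IFI checklist and blinded central review (Sections 9.3.2 and 10.2). Neither Section 9.3.5 nor Section 11 says that IFI or death from IFI is left out of the adverse event count.

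Section 9.3.3 assumes 7% IFI by Day 42 in the control arm and that "the incidence of IFI is 2% with caspofungin prophylaxis".

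**The concern.** A safety comparison that includes the efficacy event mixes two effects. If caspofungin prevents severe IFI as hoped, its grade 4+ count falls for that reason alone, and a real excess of other severe events on caspofungin is partly cancelled in the same proportion. The study-committee review of adverse event profiles is required only at P < .05, so a cancelled signal may not prompt it.

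The reverse error is a significant result against the azole arm that reflects IFI and not drug toxicity. It is less serious, because the review that follows would show IFI among the events.

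Deaths have no between-arm comparison of their own. The primary analysis censors deaths without IFI, fungal-free survival combines death with IFI, and the safety test combines death with grade 4 events.

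**Working it through.** **Plan's own figure.** Over the 42-day period the hazards are −ln 0.93 = 0.0726 (azole) and −ln 0.98 = 0.0202 (caspofungin), with loss −ln 0.95 = 0.0513. Expected events per arm are 280 × λ/(λ+γ) × [1 − exp(−(λ+γ))], which gives 19.1 + 5.5 = 24.6. The hazard ratio is 0.0202/0.0726 = 0.278. Freedman's formula gives Φ(√24.6 × 0.722/1.278 − 1.96) = 79.9%, so the stated 80% reproduces. The documents state no power or background rate for the safety test, so there is no safety figure to reproduce.

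**What is counted.** A fatal IFI within 30 days of the last dose counts on the text of Table B. A non-fatal grade 4 IFI counts if the site reports it as an adverse event. That is inferred from the absence of an exclusion, not stated.

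**Inputs.**
- From the documents: IFI 7% vs 2%; 280 per arm; two-sided 0.05; about 187 per arm at the second interim analysis.
- Assumed: b, the proportion with another reportable grade 4+ event; f, the share of IFIs that reach grade 4 or 5; t, the true caspofungin toxicity excess; and how far severe IFI overlaps with other grade 4+ events.

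**Formulas.**
- Independence: azole pA = b + (1−b)(0.07f); caspofungin pC = (b+t) + (1−b−t)(0.02f).
- 70% overlap (70% of severe-IFI patients have another grade 4+ event anyway): pA = b + 0.3(0.07f); pC = b + t + 0.3(0.02f).
- Power = Φ[(pC − pA − 1.96·s0)/s1], with s0 = √(2p̄(1−p̄)/n) and s1 = √[(pA(1−pA) + pC(1−pC))/n].

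**One look, n = 280, b = 30%, t = 10 points.** For f = 0: s0 = √(2×0.35×0.65/280) = 0.0403 and s1 = √((0.21+0.24)/280) = 0.0401, so power = Φ[(0.100 − 0.0790)/0.0401] = 70%.

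| f | Overlap | Azole | Caspofungin | Net excess | Power |
|---|---|---|---|---|---|
| 0 | none needed | 30.0% | 40.0% | 10.0 points | 70% |
| 0.5 | independent | 32.45% | 40.6% | 8.15 points | 52% |
| 1 | independent | 34.9% | 41.2% | 6.3 points | 34% |
| 0.5 | 70% | 31.05% | 40.3% | 9.25 points | 63% |
| 1 | 70% | 32.1% | 40.6% | 8.5 points | 55% |

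Under independence, power at f = 0 / 0.5 / 1 is 91 / 68 / 36% at b = 10%, 78 / 56 / 33% at b = 20%, and 66 / 54 / 42% at b = 50%. With 187 per arm and b = 30% it is 53 / 37 / 24%.

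**No toxicity difference, b = 30%, f = 1, one look.** Independence gives 34.9% vs 31.4%, and a flag in either direction in 14% of trials. With 70% overlap the proportions are 32.1% vs 30.6% and the rate is 7%. The nominal rate is 5%.

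**Repeated looks.** Simulated looks at 34, 69, 104, 172, 241 and 280 per arm (an assumption based on 138 patients a year), with b = 30% and independence, give an any-look false flag rate of about 17% at f = 0 and 28% at f = 1. Any-look power for the 10-point excess is about 78 / 62 / 46% at f = 0 / 0.5 / 1.

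**Deaths, illustration only.** Mortality of 5% vs 11% has 75% power as its own test at 280 per arm. Inside the composite the contrast is b vs b + 0.06(1−b), with power about 19% at b = 30% and 11% at b = 50%, if the excess deaths overlap grade 4 events at the background rate.

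**The case against.** The strongest reply is that the test is informal and closes nothing. The DSMC sees the study data on schedule whatever the P value, single cases are reported through CTEP-AERS, and a flag against the azole arm leads to a review in which IFI would be visible. This stands. A reader might infer that the DSMC could not recognise toxicity at all, or that the test result could never be read. Section 9.3.5 does not support that: P < .05 adds a required committee review, and its absence prevents none of the others.

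Second, IFI has its own capture route, and whether sites also enter it as an adverse event depends on case report forms held outside these documents. Under Section 8.1, an institutional diagnosis of proven or probable IFI ends protocol therapy. The 30-day window for deaths then starts near diagnosis, and later IFI deaths fall outside it unless attributed to the drug. This also stands, and it makes f = 1 a ceiling.

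Third, the background rate, f, the 10-point excess and the mortality example are not in the documents, and independence is the assumption that makes the effect largest here. At 70% overlap the power loss is roughly 7 to 15 points instead of 18 to 36. Section 9.3.4 expects death before Day +42 to be rare, so 5% vs 11% is not a forecast.

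These points limit the size. They do not remove the mechanism: nothing excludes IFI, the planned difference runs one way, and the required profile review depends on P < .05.

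**Conclusion.** The point holds as a cheap improvement. Nothing here is contradictory, and no efficacy inference or stopping boundary is affected. The single between-arm safety comparison can carry an efficacy difference of up to 5 points (7% − 2%) in caspofungin's favour. Five points is the ceiling on the Day 42 assumptions, reached only if every IFI is grade 4 or 5, is reported as an adverse event, and occurs in a patient with no other such event.

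On the assumptions above (one look, 280 per arm, 30% background, true 10-point excess), power falls from 70% to between 63% and 34%. The direction is the same at every background and severity share examined above zero, but the amount is a range and not an estimate. With no toxicity difference and all IFIs grade 4+, the single-look flag rate is about 7–14% instead of 5%. It is tempting to read 14% against 5% as rates for the whole trial. They are not: the looks are repeated without adjustment, and the trial-level rate is above 5% even with no IFI counted.

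**What to change.** In Section 9.3.5, keep the all-event test as the main safety comparison. Add two rows to the same DSMC report, with the same P < .05 referral to review:

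1. Patients with any grade 4+ event other than proven or probable IFI or death from IFI. Use the blinded central classification where it exists, and otherwise the institutional status marked as provisional.
2. Deaths from any cause by arm, also tabulated by cause.

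The rows draw on data already collected, and the text change is a sentence or two. There are three costs. Two more unadjusted tests at each look produce more false referrals, each leading only to a review. Grade 4 organ events secondary to IFI stay in row 1, so the contamination is reduced and not removed, and the f = 0 power would not be fully recovered. Provisional IFI status comes from unblinded sites in an open-label trial, which is why the all-event test should remain the main comparison.

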9.4 Gender and Minority Accrual Estimates

The gender and minority distribution of the study population is expected to be:

| Accrual Targets | | | |
|---|-------------------|--------------|--------------|
| Ethnic Category | Sex/Gender | | |
| | Females | Males | Total |
| Hispanic or Latino | 66 | 96 | 162 |
| Not Hispanic or Latino | 179 | 249 | 428 |
| Ethnic Category: Total of all subjects | 245 | 345 | 590 |
| Racial Category | | | |
| American Indian or Alaskan Native | 0 | 0 | 0 |
| Asian | 5 | 9 | 14 |
| Black or African American | 24 | 29 | 53 |
| Native Hawaiian or other Pacific Islander | 0 | 0 | 0 |
| White | 216 | 307 | 523 |
| Racial Category: Total of all subjects | 245 | 345 | 590 |

This distribution was derived from ASCT0431.

10.0 EVALUATION CRITERIA

10.1 Common Terminology Criteria for Adverse Events (CTCAE)

This study will utilize version 4.0 of the CTCAE of the National Cancer Institute (NCI) for toxicity and performance reporting. A copy of the CTCAE version 4.0 can be downloaded from the CTEP website (http://ctep.cancer.gov/protocolDevelopment/electronic_applications/ctc.htm). Additionally, toxicities are to be reported on the appropriate data collection forms.

Please note: 'CTCAE v4.0' is understood to represent the most current version of CTCAE v4.0 as referenced on the CTEP website (i.e. v4.02 and all subsequent iterations prior to version 5.0).

10.2 IFI Checklist: Submission & Central Review

Institutions will be provided with CRA worksheets (IFI Checklist) to complete which will help to identify whether patients had an IFI. Biopsy and imaging reports are requested rather than report interpretation in order to minimize the work load for sites. An independent data review committee including infectious disease and oncology experts who are unaware of treatment assignments will review and classify all cases of proven/probable IFI by EORTC/MSG criteria.⁶⁰ The committee will then submit a Central Review CRF via eRDES.

The following IFI checklist materials will be submitted (via the Document Imaging System: [contact]) as of Day 42 and as of Day 100, only if they were performed to investigate an IFI according to local physician discretion:

- Pathology reports (including autopsy reports),
- CT scan and MRI reports,
- Fungal Gram stain and microbiology culture results,
- Non-culture mycology testing results (i.e. Histoplasma urine antigens, cryptococcal CSF and serum antigens),
- Ophthalmology exams, and
- Bronchoscopy reports.

In addition, dosing and duration of steroid exposure will be collected and entered via eRDES. All reviewers will be blinded to the patient's antifungal exposures in order to limit any bias in determining the primary and secondary endpoints.

10.3 Acute GVHD

The staging of acute GVHD will follow National Marrow Donor Program (NMDP) guidelines (Appendix III).

11.0 ADVERSE EVENT REPORTING REQUIREMENTS

11.1 Purpose

Adverse event data collection and reporting, which are required as part of every clinical trial, are done to ensure the safety of patients enrolled in the studies as well as those who will enroll in future studies using similar agents.

11.2 Determination of Reporting Requirements

Reporting requirements may include the following considerations: 1) the characteristics of the adverse event including the *grade* (severity); 2) the *relationship to the study therapy* (attribution); and 3) the *prior experience* (expectedness) of the adverse event.

Commercial agents are those agents not provided under an IND but obtained instead from a commercial source. In some cases an agent obtained commercially may be used for indications not included in the package label. In addition, NCI may on some occasions distribute commercial supplies for a trial. Even in these cases, the agent is still considered to be a commercial agent and the procedures described below should be followed.

Determine the prior experience Expected events are those that have been previously identified as resulting from administration of the agent. An adverse event is considered *unexpected*, for reporting purposes only, when either the type of event or the severity of the event is not listed in:

- *the current known toxicities for each commercial agent as provided in the Drug Information for Commercial Agents Used by the Children's Oncology Group posted on the COG website; or*
- *the drug package insert.*

Secondary Malignancy

A *secondary malignancy* is a cancer caused by treatment for a previous malignancy (eg, treatment with investigational agent/intervention, radiation or chemotherapy). A metastasis of the initial neoplasm is not considered a secondary malignancy.

All secondary malignancies that occur following treatment need to be reported via CTEP-AERS. Three options are available to describe the event:

- Leukemia secondary to oncology chemotherapy
- Myelodysplastic syndrome
- Treatment related secondary malignancy

11.3 Reporting of Adverse Events for Commercial Agents - via CTEP-AERS

Expedited AE reporting must use CTEP-AERS (Adverse Event Expedited Reporting System), accessed via <https://eapps-ctep.nci.nih.gov/ctepaers>

Commercial reporting requirements are provided in Table B. The commercial agent(s) used in this study are listed in the front of this protocol immediately following the Study Committee roster.

- COG requires the CTEP-AERS report to be submitted **within 7 calendar days** of learning of the event.
- Use the NCI protocol number and the protocol-specific patient ID provided during trial registration on all reports.

CTCAE term (AE description) and grade: The descriptions and grading scales found in the NCI Common Terminology Criteria for Adverse Events (CTCAE) version 4.0 will be utilized for AE reporting and are located on the CTEP website at:

http://ctep.cancer.gov/protocolDevelopment/electronic_applications/ctc.htm. All appropriate treatment areas should have access to a copy of the CTCAE.

Table B

Reporting requirements for adverse events experienced by patients on study who have NOT received any doses of an investigational agent on this study.

CTEP-AERS Reporting Requirements for Adverse Events That Occur During Therapy with a Commercial Agent or Within 30 Days¹

| Attribution | Grade 4 | | Grade 5 |
|------------------------------|------------|----------|-----------|
| | Unexpected | Expected | |
| Unrelated or Unlikely | | | CTEP-AERS |
| Possible, Probable, Definite | CTEP-AERS | | CTEP-AERS |

¹This includes all deaths within 30 days of the last dose of treatment with a commercial agent, regardless of attribution. Any death that occurs more than 30 days after the last dose of treatment with a commercial agent which can be attributed (possibly, probably, or definitely) to the agent and is not due to cancer recurrence must be reported via **CTEP-AERS**.

11.4 Routine Adverse Event Reporting

Note: The guidelines below are for routine reporting of study specific adverse events on the COG case report forms and do not affect the requirements for **CTEP-AERS** S reporting.

The NCI defines both routine and expedited AE reporting. Routine reporting is accomplished via the Adverse Event (AE) Case Report Form (CRF) within the study database. For this study, routine reporting will include all toxicities reported via **CTEP-AERS** and all Grade 4 and higher non-hematological Adverse Events.

12.0 RECORDS AND REPORTING

See the Case Report Forms posted on the COG web site with each protocol under “*Data Collection/Specimens*”. A submission schedule is included.

12.1 CDUS

This study will be monitored by the Clinical Data Update System (CDUS). Cumulative CDUS data will be submitted quarterly to CTEP by electronic means. Reports are due January 31, April 30, July 31 and October 31. This is not a responsibility of institutions participating in this trial.

13.0 PROSPECTIVE EVALUATION OF (1→3) BETA-D GLUCAN ASSAY AS A DIAGNOSTIC TOOL FOR INVASIVE FUNGAL INFECTION IN CHILDREN UNDERGOING ALLOGENEIC HCT RECEIVING FUNGAL PROPHYLAXIS. (FOR PATIENTS THAT CONSENT ONLY)

13.1 Background

The crippling mortality associated with IFI in HCT recipients is in part related to the difficulty in diagnosing them in a reasonable time frame. In fact, IFI are frequently only diagnosed on autopsy.⁶¹ As noted above, almost all major pediatric HCT centers prescribe some form of antifungal prophylaxis during periods of immune suppression. Fluconazole is frequently used but it does not have activity against mold organisms such as *Aspergillus*. This fact has led many to theorize that using an antifungal agent with anti-*Aspergillus* activity would provide additional benefits. However, the studies comparing fluconazole to a mold active agent have been conflicting.^{3,19,42} In an effort to standardize antifungal prophylaxis, the parent randomized clinical trial described above will compare the efficacy of an azole agent (voriconazole or fluconazole) to that of caspofungin. This study will potentially define the appropriate antifungal prophylactic agent.

Regardless of the antifungal agent ultimately chosen, prophylaxis will not prevent all IFI. In those patients with a breakthrough IFI, a modification to the antifungal regimen will be necessary. The challenge is to identify those patients sustaining breakthrough IFI at the earliest possible point. The recent Infectious Disease Society of America (IDSA) guidelines for fever and neutropenia suggests a pre-emptive therapeutic approach.⁶² This approach requires the use of adjunctive diagnostic biomarker assays such as the Fungitell Assay, to help inform the decision to modify antifungal therapy. The utility of this assay has been well defined in adult immunocompromised patients but to date there are limited data on the operating characteristics of this assay in pediatric patients undergoing HCT and receiving antifungal prophylaxis. In order to endorse this as a useful adjunctive study, the operating characteristics must be defined in a high-risk pediatric population. We propose to prospectively study this biomarker in the parent COG trial. This parent study cohort provides a one-time opportunity to rigorously evaluate the ability of this fungal biomarker to identify IFI in a homogeneous cohort of pediatric HCT patients receiving antifungal prophylaxis. Knowledge of the operating characteristics of the Fungitell Assay under these study conditions is necessary to inform its potential future utility.

13.1.2 Traditional diagnostic studies to identify patients with suspected IFI

Traditional diagnostic modalities for IFI are limited to radiologic imaging and blood or tissue culture techniques. Radiologic studies may show visceral involvement but an invasive biopsy procedure is necessary to differentiate between a fungal or non-fungal infectious process. Although blood cultures may be used to isolate *Candida* spp. during candidemia, they are not helpful in the setting of invasive candidiasis without fungemia. Furthermore, traditional blood cultures are not typically successful at isolating mold infections such as *Aspergillus*. Cultures of tissue specimens can be definitive but require invasive techniques for sample procurement.

